3.2.7 Analysis of Additional Outcomes

The additional outcomes for this study are as follows:

- Mean low back VAS pain score over time through the 24-month interval
- Mean lower extremity (right and left leg) VAS scores over time through the 24-month interval
- Mean ODI score over time through the 24-month interval
- Fusion at the 12-month and the 24-month interval
- Occurrence of device-related Serious Adverse Events through the 24-month interval
- Occurrence of study-related Adverse Events through the 24-month interval
- Neurological status assessment (strength, sensation, and reflexes) over time through the 24-month interval (reporting categorized as improved, maintained, or reduced with new or increased neurological deficit being further categorized as transient (< 3 months/90 days) or longer term \geq 3 months/90 days);

- Radiographic data observed over time specific to the index level (translation, angulation, disc height, and device position)
- Subject satisfaction with procedure/outcome
- Work status over time
- Pain medication use over time
- Operative time
- Estimated blood loss
- Duration of hospitalization
- Graft site pain (as applicable)
- Adjacent segment status at 24-months post-operative assessed by quantitative and qualitative radiographic data (translation, angulation, and disc height)

The mean low back pain score over time through the 24-month interval will be summarized using descriptive statistics and a 95% confidence interval based upon the t-distribution. The mean lower extremity (right and left leg) VAS scores over time and the mean ODI score over time will be analyzed in the same manner.

The number and percentage of subjects achieving fusion at the 12-month and 24-month intervals and the corresponding 95% exact (Clopper-Pearson) confidence intervals for the true proportion of subjects achieving fusion will be presented.

The number and percentage of subjects with any device-related serious adverse events (SAEs) and with any study-related adverse events will be presented, together with 95% exact (Clopper-Pearson) confidence intervals for the true proportions. AEs will be summarized at the subject level by type of event using frequencies and percentages. AEs will also be tabulated at the event level by severity and by relatedness.

Neurological status for strength, sensation, and reflexes will be summarized by time point using counts and percentages and 95% exact (Clopper-Pearson) confidence intervals for the true proportions.

Radiographic data for translation, angulation, and disc height specific to the index level will be summarized by time point using descriptive statistics and a 95% confidence interval based upon the t-distribution. Device position will be summarized by time point using counts and percentages and 95% exact (Clopper-Pearson) confidence intervals for the true proportions.

Subject satisfaction with the procedure/outcome will be summarized using counts and percentages and 95% exact (Clopper-Pearson) confidence intervals for the true proportions.

Operative time, estimated blood loss, and duration of hospitalization will be summarized using descriptive statistics and a 95% confidence interval based upon the t-distribution. Work status, pain medication use, and graft site pain will be summarized by time point using frequencies and percentages and 95% exact (Clopper-Pearson) confidence intervals for the true proportions.

Radiographic data at 24-months post-operative for translation, angulation, and disc height for treated and adjacent segments will be summarized using descriptive statistics and a 95% confidence interval based upon the t-distribution.

For the analyses of these additional outcomes, there will be no imputation of missing values.

3.2.8 *Data Management Plan*

The purpose of a Data Management Plan (DMP) is to provide guidance for all aspects of data management as it pertains to this investigation. A DMP shall be in place prior to the initiation of this clinical investigation.

3.2.9 *Subject Withdrawal*

An enrolled subject is considered “withdrawn” from the investigation if their participation in the study is discontinued for any reason after signing the consent form. If a subject chooses to withdraw from the investigation, a Subject Discontinuation CRF will be completed and submitted to the sponsor as soon as it is practical. Every effort will be made to complete the trial CRFs applicable up to the point of withdrawal. If a subject voluntarily withdraws from the investigation, the data generated from their participation in the study will still be used in the overall investigation data set. Approval to use the data will be documented in the consent form.

Subjects who have not voluntarily withdrawn from the investigation, but fail to return for follow-up visits, will be considered “Lost-to-Follow-Up” (LTFU). Subjects identified as LTFU will be withdrawn from the investigation through completion of a Subject Discontinuation Form. Prior to formally discontinuing a subject from the investigation for being LTFU, multiple efforts shall be made including supplemental attempts to contact the subject. As an example, supplemental efforts may include 3 attempts to reach this subject (2 by telephone and 1 by certified letter). All supplemental attempts to reach a potential LTFU subject shall be documented in writing.

3.2.10 *Control Subject Population*

The SCOUT IDE Investigation is a single-arm clinical trial. Accordingly, a control study population is not undertaken for this investigation as each study subject essentially functions as their own control in terms of outcome parameters over time.

3.2.11 *Randomization*

This is NOT a randomized investigation. All enrolled study subjects shall be treated with the investigation device (SIFS mesh).

3.2.12 *Minimization of Bias*

To minimize the introduction of bias into this clinical investigation, the following measures will be observed:

- All investigation participants shall be enrolled under the same inclusion/exclusion criteria,
- All investigation participants shall follow the same study protocol,
- Adverse event adjudication will be performed by an objective Data Monitoring Committee panel.

The study entrance criteria for this investigation are designed to accommodate enrollment of a study population that would closely match the intended patient population for the device. Following determination that a subject is eligible for study participation and the approved Informed Consent Form (ICF) for the investigative site is signed, a subject is considered enrolled into the SCOUT clinical investigation. All study subjects will receive the investigational treatment device (SIFS mesh).

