3.2.3 Statistical Methods

The statistical analysis of the data obtained from this study will be performed using SAS® version 9.1 or higher. All statistical tests will be performed at the 0.05 significance level, unless otherwise indicated.

Data collected in this study will be documented using summary tables and subject data listings. Continuous variables will be summarized using descriptive statistics, specifically the mean, median, standard deviation, minimum, and maximum, and a 95% confidence interval for the mean based

on the t-distribution. Categorical variables will be summarized using frequencies and percentages and 95% exact (Clopper-Pearson) confidence intervals for the true proportions.

All analyses of effectiveness and safety will be based upon the Treated Population defined to be all treated subjects.

3.2.4 *Determination of Sample Size*

The required sample size was calculated based on the following specifications:

1. Endpoint: success rate
2. One-sided exact binomial test for a binomial proportion
3. Alpha = 0.05
4. True percentage of successes = 68%
5. Performance Goal (null percentage of successes) = 55%
6. Power = 80%

The required sample size based upon these specifications is 87 subjects. The sample size was increased to 102 subjects to take into account an assumed 15% lost to follow-up rate.

3.2.5 *Sample Size Re-Estimation*

A sample size re-estimation will be performed based on 12-month interim data.

3.2.6 *Analysis of Primary Endpoint*

The primary endpoint for this investigation is a composite endpoint of pain, function, fusion, and safety that meets all of the following criteria at the 24-month study interval:

- Pain – Improvement in low back pain score evidenced by a 20 mm reduction on a 100 mm Visual Analog Scale (VAS) when compared to baseline (Note: a lower VAS pain score indicates less pain),
- Function – Improvement in low back function evidenced by a 15 point decrease of the Oswestry Disability Index (ODI) score compared to baseline. (Note: a higher ODI score indicates greater disability with respect to low back function),
- Fusion – Bridging bone demonstrated on CT Scan
- Safety – Freedom from investigational device-related Serious Adverse Events at the index level through the 24-month study interval.

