8.0 SAFETY EVALUATION

Safety of the Spineology Interbody Fusion System will be determined through the reporting process for Adverse Events. All adverse events, whether felt to be device-related or not, are to be reported and followed at each study interval to resolution, or for events that remain unresolved, until the subject concludes study participation. Information captured will include the type and description of the event, date of onset, treatment required and resolution status. The investigator shall additionally provide any supplemental information pertinent to the overall evaluation of the event. All reported events will be reviewed and adjudicated by an independent Data Monitoring Committee (DMC)/Clinical Events Committee (CEC).

For this investigation, an adverse event is defined as a secondary disease or condition that develops in addition to, or at an increased rate or severity from, the expected response to treatment, necessitating further evaluation and treatment by a physician. An adverse event may be an undesirable clinical occurrence, subject complaint, change in health status, or product issue. A clinical event will not be reported if it existed at the time of enrollment and continued unchanged thereafter, unless the event worsened considerably requiring additional medical or pharmacological treatment. Adverse Event reporting begins during the study treatment surgical procedure.

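### Section 3.2.7 reports 24-month adverse event rates as crude percentages of all treated subjects, which tends to understate them modestly if subjects are lost to follow-up

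*Combined protocol and SAP*

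**What the plan says.** Section 3.2.7 lists two safety outcomes with a fixed horizon: "Occurrence of device-related Serious Adverse Events through the 24-month interval" and "Occurrence of study-related Adverse Events through the 24-month interval". The planned summary is: "The number and percentage of subjects with any device-related serious adverse events (SAEs) and with any study-related adverse events will be presented". Both percentages are to carry exact 95% binomial intervals by the Clopper-Pearson method.

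Three other statements determine how that percentage is formed:

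- Denominator, section 3.2.3: "All analyses of effectiveness and safety will be based upon the Treated Population defined to be all treated subjects".
- Missing data, end of section 3.2.7: "For the analyses of these additional outcomes, there will be no imputation of missing values".
- Expected loss, section 3.2.4: "The sample size was increased to 102 subjects to take into account an assumed 15% lost to follow-up rate".

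Under section 3.2.9, subjects lost to follow-up are withdrawn. Under section 8.0, follow-up of events ends when participation ends. Onset is recorded: "Information captured will include the type and description of the event, date of onset, treatment required and resolution status". The document contains no time-to-event, person-time or number-at-risk summary of adverse events.

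**The concern.** A binomial proportion with an exact interval presumes that every subject's 24-month status is known. For a subject who leaves at month 5 without an event, it is known only to month 5. The planned rule nevertheless gives that subject full weight in the denominator and no chance of adding a later event to the numerator. What is estimated is the proportion with an event seen while under observation, not the 24-month proportion.

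This deserves attention for three reasons. Section 2.1 names safety alongside effectiveness as the purpose of the study. Section 3.1 says that the data will support a regulatory submission. With a single arm, no comparator shares the shortfall. The plan also handles the same gap differently elsewhere: section 3.2.6 treats a missing Month 24 composite, which includes freedom from device-related SAEs, as missing and imputes it.

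**Working it through.** **The plan's own figure.** Section 3.2.4 gives 87 evaluable subjects. With n = 87 and success declared at 56 or more, the exact one-sided test of 55% has size 0.0487 and power 0.801 at 68%, so 87 reproduces. Inflation gives 87 / 0.85 = 102.4, stated as 102. The plan therefore allows for about 0.15 × 102 = 15 lost subjects.

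**Inputs.** From the documents: denominator 102 treated, loss 15%, horizon 24 months. Assumed, because the documents are silent: the true 24-month risk q, the share f of events that occur before anyone is lost, the timing of loss, and loss unrelated to event risk.

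**Formula.** Let G(t) be the share still followed at month t. With the remaining events spread evenly over the period in which loss can occur,

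expected crude proportion = q × [f + (1 − f) × mean of G(t)].

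For loss spread evenly over 24 months, G(t) = 1 − 0.15t/24, with mean 1 − 0.15/2 = 0.925. For loss spread evenly over months 12 to 24 only, the mean is (1 + 0.925)/2 = 0.9625.

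| Scenario (15% lost) | Multiplier of q | True 10% shows as |
|---|---|---|
| Even loss, events evenly spread (f = 0) | 0.925 | 9.25% |
| Even loss, half of events before any loss | 0.5 + 0.5 × 0.925 = 0.9625 | 9.6% |
| Even loss, 80% of events before any loss | 0.8 + 0.2 × 0.925 = 0.985 | 9.85% |
| Loss only after month 12, f = 0 | 0.9625 | 9.6% |
| Bound: all 15% lost at day 0, f = 0 | 0.85 | 8.5% |

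**Constant hazard as a check.** With C the time of loss, expected crude = 0.85q + 0.15 × [1 − E(exp(−λC))], where λ = −ln(1 − q)/24. For q = 20% and even loss over 24 months, E = 0.20/0.2231 = 0.896, giving 0.170 + 0.0156 = 18.6%. For q = 40% the result is 37.3%. If all losses fall in the first 6 months, 20% shows as 17.4%, about 13% too low in relative terms.

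**Against the planned interval.** Ten events in 102 give a Clopper-Pearson interval of 4.8% to 17.3%, which is wide beside a shift of 0.75 points or less. With constant hazard and even loss, coverage of the true rate at 5, 10, 20 and 40% is 98.4, 95.2, 95.0 and 93.6%. If all losses fall in the first 6 months, coverage drops to 91.8% at a true 20% and 85.6% at a true 40%. With no events, the upper limit is 3.6% on 102 subjects and 4.2% on 87.

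**The case against.** **Little rests on these percentages.** Section 3.2.2 calls the additional outcomes descriptive, and they carry no hypothesis or threshold. The safety criterion that is tested sits inside the composite, whose missing values are handled separately in section 3.2.6. This stands, and it limits the weight of the point.

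**The larger figures need unfavourable inputs.** Event recording starts during surgery (section 8.0), and section 7.2.3 lists many operative and incisional risks that would tend to arise before anyone is lost. A reader might take 7% to 13% as the expected shortfall. The documents do not support that: it needs a constant hazard over two years and, for 13%, all loss within six months. Nor are 15% of events missed. The 15% is a planning allowance, and only events after departure go unseen.

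**The classification of lost subjects is inferred.** The plan never says that they count as event-free. A reader might conclude that the planned percentages always flatter the device. That holds under the all-treated reading, where unseen events can only lower the count. If the bar on imputation instead meant dropping event-free lost subjects, the error could reverse. With even loss, evenly spread events and q = 10%, the numerator share is 0.85 × 0.10 + 0.15 × 0.05 = 0.0925. The denominator share is 1 − 0.15 × 0.95 = 0.8575, and the ratio is 10.8%. Section 3.2.3 favours the all-treated reading, but section 3.2.7 should say so.

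**Kaplan-Meier also assumes non-informative loss.** Correct. It does not repair the case in which subjects with complications leave more often.

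**Conclusion.** The point holds at modest size. Under the all-treated reading, the planned percentages tend to understate the 24-month proportions. If 15% are lost and loss is non-informative, the understatement is about 1.5% to 7.5% of the true rate in plausible scenarios and at most 15%. At a true 10% rate that is 0.15 to 0.75 points, and at most 1.5 points. It could be larger if loss is related to complications.

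The range rests on assumed event rates, event timing and loss timing, and scales with the loss actually seen. In most of the scenarios examined the exact interval keeps close to its nominal coverage. The primary test is unaffected. A reader might infer that the study's safety conclusion is invalid, but the documents do not support that, because no decision rule uses these rates. The change is worth making because the remedy uses dates already collected and the shortfall has no control arm to offset it.

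**What to change.** In section 3.2.7:

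- Keep the crude counts and percentages, and state how subjects with incomplete follow-up are classified in them.
- Add the 24-month cumulative incidence with a 95% interval for first device-related SAE and for first study-related AE, censored at the last AE assessment. Use Kaplan-Meier, or Aalen-Johansen if deaths occur that are not themselves the event being counted.
- Show the number still followed at each visit.
- State the non-informative censoring assumption.

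The onset dates, scheduled AE assessments and discontinuation forms already supply the data. The cost is a few sentences and one table. The drawbacks are slightly less favourable rates and an added assumption that cannot be verified from the data.

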4.2 INCLUSION CRITERIA

To participate in this investigation, a study subject shall meet all of the following inclusion criteria:

- Minimum age of twenty-one (21) years but not greater than eighty (80) years;
- Skeletally mature;
- Have a confirmed diagnosis of lumbar degenerative disc disease requiring single-level fusion between L2 and S1. Lumbar DDD diagnosis confirmation shall be determined by subject history, physical examination, and radiographic studies with one or more of the following factors:
 - Instability as defined by >3mm translation or $\geq 5^\circ$ angulation;
 - Osteophyte formation of facet joints or vertebral endplates;
 - Decreased disc height, on average by > 2mm, but dependent upon the spinal level;
 - Scarring/thickening of the ligamentum flavum, annulus fibrosis, or facet joint capsule;
 - Herniated nucleus pulposus;
 - Facet joint degeneration/changes; and/or
 - Vacuum phenomenon;
- Report pre-operative low back pain score of ≥ 40 mm on a 100mm Visual Analog Scale (VAS) correlating with involved level;
- Report pre-operative Oswestry Disability Index (ODI) score of ≥ 40 ;
- Received at least 6 months of conservative (non-surgical) treatment without sufficient relief from symptoms;
- Willing and able to comply with follow-up evaluations per protocol, including completion of self-assessment survey questionnaire(s), and has read,

understood and signed the sponsor and IRB approved site-specific informed consent form.

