Patient Survey – This survey form collects subjective data consisting of pain rating on a Visual Analog Scale (VAS) for the low back, right leg, left leg and iliac crest as applicable (iliac crest completed at post-op intervals only for subject who underwent iliac crest graft harvest). The survey additionally contains a 10-question Oswestry Disability Index (ODI) to assess low back function and an SF-36 health questionnaire to assess mental and physical components. Lastly, this form allows the subject to rate their level of satisfaction with their surgical outcome and is to be completed only at the post-op follow-up intervals. The eCRF should be entered in the EDC system within 10 working days of the study visit date.

Pain Medication Log – The pain medication log shall be completed at baseline and reviewed at each subsequent study interval follow-up examination. The log shall be updated for changes in pain medication use (start, stop, changes in dosing) as compared to the previous study interval visit. Beyond identifying the prescription information (i.e. medication name, strength and frequency of use), the site shall specify if the pain medication is prescribed for treatment of low back pain or for other reasons. The eLog should be reviewed/updated in the EDC system within 10 working days of the study visit date.

Neurological Evaluation – This form captures relevant neurological testing for the lumbar spine (L2 – S1). Neurological testing includes assessment of bilateral lower extremity deep tendon reflexes (knee and ankle), muscle strength tested against resistance (hips, knees, ankles, and feet), and lumbosacral dermatome sensation (low back, thighs, calves, and feet). The eCRF should be entered in the EDC system within 10 working days of the study visit.

Surgery/Hospitalization – This form records relevant information regarding the study procedure including hospitalization duration, device detail, supplemental fixation detail and operative/intraoperative/postoperative findings. The eCRF should be entered in the EDC system within 10 working days of the subject discharge date.

Follow-Up Evaluation – This form captures relevant information regarding postoperative subject medical care, tobacco use, alcohol consumption, work status and occurrence of adverse events. The eCRF should be entered in the EDC system within 10 working days of the study visit.

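### Section 3.2.7 reports pain medication use and work status only as visit percentages, which cannot show how many subjects stopped or started medication, or returned to or left work; baseline-to-visit shift tables would.

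*Combined protocol and SAP*

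**What the plan says.** Section 3.2.7 covers both outcomes in one sentence: "Work status, pain medication use, and graft site pain will be summarized by time point using frequencies and percentages", with Clopper-Pearson intervals. Section 3.2.3 sets the population: "All analyses of effectiveness and safety will be based upon the Treated Population defined to be all treated subjects". Section 3.2.7 then adds: "For the analyses of these additional outcomes, there will be no imputation of missing values".

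Section 3.2.10 explains the absence of a control arm by saying that "each study subject essentially functions as their own control in terms of outcome parameters over time".

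Section 10.0 describes what is collected. The Pain Medication Log holds drug name, strength and frequency, and "the site shall specify if the pain medication is prescribed for treatment of low back pain or for other reasons". It is also kept current between visits: "The log shall be updated for changes in pain medication use (start, stop, changes in dosing) as compared to the previous study interval visit". Work status is on the baseline history form and the Follow-Up Evaluation form. Table 1 schedules both items at baseline and at every post-discharge visit through 24 months, but not at the surgery and hospitalization interval.

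Section 4.2 admits a wide age range: "Minimum age of twenty-one (21) years but not greater than eighty (80) years".

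Nowhere do the documents define pain medication use as a variable, say how the indication flag enters the analysis, set a workforce denominator, or plan a table of baseline status against later status for these two outcomes.

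**The concern.** In a single-arm study these outcomes offer one contrast: each subject against his or her own baseline. Section 3.2.10 relies on that contrast, but the planned tables for medication and work do not make it. They set one percentage beside another, so subjects who improve cancel subjects who worsen. Elsewhere the protocol does use within-subject change: pain and function success are changes from baseline, and neurological status is reported as improved, maintained or reduced.

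The definitions are a second gap. An analgesic taken for another joint and one taken for the back mean different things after a lumbar fusion, and the log separates them. Likewise, a retired subject cannot be counted as failing to return to work. If the tables ignore these distinctions, the reported change mixes subjects who could change with subjects who could not.

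At stake is how these two outcomes are read. The pain criterion in Section 3.2.1 takes no account of analgesics, so a subject-level view of back-pain medication helps show whether pain relief came with less drug use or more.

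**Working it through.** **Figures in the plan.** The documents give no expected rate for medication use or employment, so there is no planned figure to reproduce for these outcomes. The evaluable number, 87 (Section 3.2.4), is used below only as a table size. It reproduces: an exact one-sided binomial test of 55% against 68% with n = 87 rejects at 56 or more successes, with type I error 0.0487 and power 0.801. Every rate below is an assumption.

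**1. What visit percentages leave open.** Let b subjects of n be users at baseline and f at follow-up, with s stopping and t starting. Then f = b − s + t, so s = (b − f) + t, where t is at most n − b and s is at most b.

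- Medication, n = 87, b = 70, f = 35 (about 80% and 40%): s = 35 + t and t ≤ 87 − 70 = 17. So 35 to 52 subjects stopped (35/70 = 50% to 52/70 = 74% of baseline users), and 0 to 17 of the 17 baseline non-users started.
- Work, n = 87, 44 working at both visits: the number who stopped equals the number who began, anywhere from 0 to 87 − 44 = 43.

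Each range gives identical visit percentages and identical exact intervals. A two-by-two table of baseline status against visit status would give s and t directly.

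**2. Different subjects at different visits.** Section 3.2.4 enrols 102 and allows 15% loss, so about 102 − 87 = 15 subjects may be absent at Month 24. Suppose 82 of 102 (80%) use medication at baseline. If all 15 lost subjects were users, the baseline rate among the remaining 87 is (82 − 15)/87 = 67/87 = 77%. If none were, it is 82/87 = 94%. With no imputation, part of any difference between the baseline and Month 24 percentages can come from who is missing.

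**3. What would follow if the indication flag were not used.** Let low-back use be p, and let a share q take a pain drug for another reason, independently of back use. Any-reason use is 1 − (1 − p)(1 − q). If q is stable, the change is (1 − q) times the low-back change. For an assumed fall from 80% to 40%:

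| q | Baseline | Follow-up | Fall (points) |
|---|---|---|---|
| 0% | 80% | 40% | 40 |
| 10% | 82% | 46% | 36 |
| 20% | 84% | 52% | 32 |
| 30% | 86% | 58% | 28 |
| 40% | 88% | 64% | 24 |

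Stability of q matters. If q falls from 30% to 10%, the table reads 86% to 46%, a fall of 40 points and no dilution. If q rises from 10% to 30%, it reads 82% to 58%, a fall of 24 points.

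**4. What would follow if work status had no line for subjects outside the workforce.** If a share w is outside, the all-subject change is (1 − w) times the workforce change. For an assumed rise from 50% to 75% (25 points), w = 10%, 20%, 30% and 50% give 22.5, 20, 17.5 and 12.5 points.

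**The case against.** The strongest reply is that these are two of 16 additional outcomes for which Section 3.2.2 promises only description. No hypothesis, error rate or success criterion rests on them, and visit percentages with exact intervals are a legitimate summary. Own-baseline comparison is already built into the primary endpoint. All of that stands, and it makes this a minor point.

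Four stronger readings are tempting, and the documents do not support them.

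- *Drugs for other conditions are counted.* The plan does not say so. It is silent, and the flag in the log suggests that a split may have been intended.
- *Retired subjects dilute the work-status result.* The answer categories are on case report forms that are not in the text. If there is a retired or not-employed category, the planned frequencies would show it on its own line.
- *Within-subject change is lost.* It is absent from the named summary tables only. Section 3.2.3 also plans subject data listings, and the log records each start, stop and dosing change.
- *The change is understated.* No rate in the documents allows this to be shown. The proportional result needs stable, independent use for other reasons; step 3 shows that it can vanish when that use shifts.

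An own-baseline table also needs care. Classing a subject as reduced or increased across different drugs needs a rule that the plan does not contain. Section 10.0 speaks of prescription information, so it is unclear whether over-the-counter analgesics are logged. A careless workforce definition could drop subjects who are off work because of their backs.

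The objection does not answer step 1: no set of visit percentages, however categorised, identifies how many subjects changed in each direction.

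**Conclusion.** The point holds as a minor improvement. The planned summaries cannot separate stopping from starting medication, or returning to work from leaving it, and may compare different subjects across visits. This follows from the form of the tables and needs no assumed rate. The ranges of 35 to 52 stopping with 0 to 17 starting, and of 0 to 43 leaving work, only illustrate how wide the ambiguity can be.

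The definitional gap is conditional. If all drugs are counted, or if subjects outside the workforce have no separate line, the change would be diluted under stable conditions. The documents do not allow the amount to be computed, and steps 3 and 4 are illustrations. The primary analysis and the 87 evaluable and 102 enrolled subjects are unaffected.

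**What to change.** Add to Section 3.2.7:

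- **Medication variable.** Base pain medication use on log entries flagged for low back pain, with any-reason use as a second line. State whether non-prescription analgesics count.
- **Medication shift table.** For each post-discharge visit through 24 months, tabulate user or non-user at baseline against user or non-user at the visit, among subjects with data at both times and with that number shown. Give exact intervals for the proportion of baseline users who stopped and of baseline non-users who started. Report dose reduction or increase only under a rule fixed in advance.
- **Work-status shift table.** Use the same layout. Put subjects retired or otherwise outside the workforce at baseline on a separate line, and keep subjects who are off work because of their back in the workforce group.

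The existing visit percentages can stay. The cost is a few lines of text and two or three descriptive tables. The log and forms already scheduled supply the data, subject to confirming that the work-status categories on the forms identify the groups above. Fixing the definitions now also avoids choosing the indication or denominator after the results are known.
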